5.1.2 Primary Outcome Definition

ATRS was assessed at baseline, 3 months, 6 months and 1-2 years post injury. The primary outcome is the change in the ATRS score from baseline to 1-2 years post injury. The last follow-up was planned 12 months post-injury, preferably at the 12 months test visit at one of the study physiotherapists. Patients that did not conduct the test battery or of some other reason did not complete the questionnaires at 12 months were contacted by phone and asked to answer the PROMs electronically via an encrypted link to the questionnaires sent by e-mail. In order to minimize loss to follow up the patients were allowed to answer the questionnaires up to 24 months post injury. This time extension was not done for the last included patients who did not answer the last set of PROM's or did not meet for the 12 months testing as the registration of completed forms and testing of patients was stopped 12 months after the last patient was included. An earlier publication reported only minor improvements occurring between the 1- and 2-year evaluations (7).

5.1.3 Secondary Outcomes Definitions

5.1.3.1 SF-36

The 36-Item Short Form Health Survey (SF-36) was assessed at baseline, 6 months and 1-2 years post injury. The PCS and MCS is composed of five and three subscales, respectively. The two SF-36 component summaries PCS and MCS in addition to the subscale physical function (PF) will be compared between the three treatment arms. As the ATRS and SF-36 are presented simultaneously, the time extension of up to 24 months post injury also applies to 12-month assessment of the SF-36 questionnaire. The difference in scores from baseline will be assessed at the 6 months and 1-2 years visits.

5.1.3.2 Re-rupture

Re-rupture is here defined as a total rupture of the same Achilles tendon as treated in the trial within the 12-month visit. Re-rupture will be treated as a dichotomous outcome. The diagnosis is done clinically without any need of imaging techniques. Re-ruptures were continuously reported to the principal investigator of the study. Patients suffering from either a re-rupture of the same Achilles tendon or a new rupture of the contralateral Achilles tendon were excluded from further testing and questionnaires.

5.1.3.3 ATRS score at intermittent visits

The change in ATRS scores from baseline to the intermittent visits (3 and 6 months) are regarded as continuous secondary endpoints.

5.1.3.4 Muscle lab measurements

The following 6 muscle lab measurement endpoint will be considered.

STATISTICAL ANALYSIS PLAN for the Achilles trial

1. Heel rise height (cm): For description see 3.
2. Hopping: A continuously rhythmical jump similar to skipping. The patients performed 25 jumps. The average air flight and floor contact times were documented, and the plyometric quotient (flight time/contact time) was used for data analysis.
3. Drop counter-movement jump (drop CMJ): The patients started by standing on one leg on a 20-cm-high wooden box. They were instructed to “fall” down onto the floor and, directly on landing, perform a maximum vertical one-legged jump. The maximum jumping height in centimeters was used for data analysis (see 1).
4. Concentric heel rise: For description see 5.
5. Eccentric-concentric heel rise: For the strength tests (4 and 5), a linear encoder was used. A spring-loaded string was connected to a sensor inside the linear encoder unit. When the string was pulled, the sensor gave a series of digital pulses proportional to the distance travelled. The resolution is approximately 1 pulse every 0.07 mm. By counting the number of pulses per time, the displacement as a function of time can be recorded and thus allow calculation of time, length, velocity, force, and power (force x velocity). In this experiment, the spring-loaded string of the linear encoder was attached to the heel of the participant’s shoe and thus the height (in centimeters) and time (in seconds) of the heel displacement of the heel-rise could be measured. The weight of the participant and the extra external weight were entered into the MuscleLab software and peak power in watts was calculated. The best trial (ie, with the highest power in watts) for each weight was used for data analysis.
6. Muscular endurance test: A standing heel-rise test. The total amount of work performed (in joules) and the maximum heel-rise height were used for data analysis.

For each of these endpoints, a similar measurement for the healthy Achilles is performed. The ratio of the test result in the treated foot versus the healthy foot is calculated and multiplied with 100. This measurement is referred to as the Limb symmetry index (LSI). These are also considered as secondary endpoints. Furthermore, the physical tests are performed both at the 6-month visit and at the 1-2 years visit, the results of which are both considered as secondary endpoints. Furthermore, the change in the test results, from the 6-month to the 1-2 years visit, are also considered secondary endpoints. Thus, there are 36 secondary endpoints relating to the physical tests.

5.1.4 Overview of Outcomes

Level	Outcome	Timeframe	Type
Primary	ATRS	1-2 years	Continuous
Secondary	SF-36	1-2 years	Continuous
	Re-rupture rate	12 months	Dichotomous
	Muscle-lab measurement system (see 5.1.3.4 for description)	6 and 1-2 years	Continuous

5.2 Analysis Methods

5.2.1 Primary Outcome

5.2.1.1 Primary Analysis

The primary outcome in this trial is the change in the ATRS score from baseline to the 1-2 years visit.

The primary analysis will be performed by applying a linear mixed effects model to model the longitudinal change from baseline ATRS measurements at the 3-month, 6-month and 1-2-year visits. A fixed interaction term between the follow-up visit and treatment group will be included in the model. The baseline ATRS measurement will be included as a fixed covariate in the model. Study centre, which was used as a stratification variable in the randomization, will also be included as a fixed covariate. An individual-specific random intercept term will be included in the model to account for the dependencies within individuals. An unstructured correlation structure will be assumed for the repeated measurements.

From the fitted model, the estimated marginal means will be computed for each time point and each treatment. Based on the estimated marginal means, an omnibus test, where the null hypothesis is that there is no difference between the three treatment groups, will be performed for the 1-2-year visit. This corresponds to step 1 in Section 2.4.1. If the test is statistically significant on the 5% level, pairwise testing between the three treatment groups will be performed for the 1-2-year visit (step 2 in Section 2.4.1). A 5% significance level will be used in each of these tests. As described in Sections 2.4.1-2.4.2, the hierarchical testing procedure maintains the overall type I error rate at 5%. The estimated marginal means with 95% confidence intervals of the change in ATRS from baseline will be presented for each of the treatment groups for the 1-2 years visit.

If the omnibus test at the 1-2 years visit does not show statistical significance, then no further hypothesis testing will be performed. However, the estimated marginal means and the accompanying 95% confidence intervals will still be presented, but should be considered as secondary analyses.

The analysis will be conducted in the FAS.

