2.3 Sample size

The sample size was based on the primary endpoint of ATRS at 1-2 years. The calculation was based on a one-way ANOVA analysis, assuming a standard deviation of 20 in each treatment group. A total sample size (study completers) of 480 (160 in each group) was deemed necessary to achieve 80%

STATISTICAL ANALYSIS PLAN for the Achilles trial

power to detect a difference of ATRS of 7 between the groups in two-sided tests at 5% significance level. To compensate for withdrawals/loss to follow-up, a total enrolment of 530 patients was targeted.

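### The primary model gives baseline ATRS one slope for all three visits, which can cost some precision at the 1-2 year visit if baseline predicts the visits differently

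*SAP*

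**What the plan says.** SAP section 5.2.1.1 defines the endpoint: "The primary outcome in this trial is the change in the ATRS score from baseline to the 1-2 years visit". A linear mixed model is used to "model the longitudinal change from baseline ATRS measurements at the 3-month, 6-month and 1-2-year visits". The fixed part contains one interaction: "A fixed interaction term between the follow-up visit and treatment group will be included in the model". Baseline and study centre enter as plain covariates; for baseline the text is "The baseline ATRS measurement will be included as a fixed covariate in the model". For the covariance, "An unstructured correlation structure will be assumed for the repeated measurements", together with a random intercept.

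The omnibus test is made at one visit only: it "will be performed for the 1-2-year visit. This corresponds to step 1 in Section 2.4.1". The pairwise tests that may follow use the same visit.

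No baseline-by-visit term appears in section 5.2.1.1 or in the later parts of section 5.2.1 on assumption checks, missing data and sensitivity analyses. If residual checks look poor, section 5.2.1.3 responds by adding more random effects.

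**The concern.** The planned visits run from about 91 days to as late as day 728 (section 2.7). The baseline score need not predict a 3-month score, taken early in recovery, in the same way as it predicts a score one to two years out. If it does not, the single slope is a weighted compromise across visits. It is then not the best slope at 1-2 years, and part of the variance that baseline could explain there is left in the residual.

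Two features of the plan do not remove this. Taking change from baseline as the response shifts every visit's slope by -1 and leaves the differences between slopes as they were. A further random effect does not give baseline a different fixed slope at each visit.

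What is at stake is some precision in the only confirmatory test. The validity of the test is not in question.

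**Working it through.** **The plan's own figure.** Section 2.3 plans a one-way ANOVA, "assuming a standard deviation of 20 in each treatment group", a difference of 7 points, two-sided 5%, 160 completers per arm and 80% power. Placing the three means at -3.5, 0 and +3.5:

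- Noncentrality = n × Σ(mean²) / SD² = 160 × (12.25 + 0 + 12.25) / 400 = 9.8.
- On 2 and 477 degrees of freedom this gives 80.4% power.
- The smallest n that reaches 80% is 159 per arm, 477 in total, so the planned 480 reproduces. The calculation takes no credit for baseline adjustment.

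**Cost of a common slope.** Let b₁, b₂, b₃ be the true baseline slopes at the three visits, S the residual covariance given baseline, and σₓ² the baseline variance. With complete data and free visit variances and correlations:

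- The common slope settles at c = (1′V⁻¹b)/(1′V⁻¹1), where V = S + (b − c1)(b − c1)′σₓ², solved by iteration.
- Variance ratio at 1-2 years, common against visit-specific slope = 1 + (b₃ − c)²σₓ² / S₃₃.

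**Assumed inputs.** The SAP gives no baseline SD, no baseline-to-follow-up correlation and no visit-to-visit correlation.

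- Visit-to-visit correlations given baseline (3 v 6 months, 3 months v 1-2 years, 6 months v 1-2 years) are taken from 0.5/0.3/0.5 to 0.8/0.7/0.8.
- The follow-up SD is 20, as in section 2.3.
- The baseline SD is set to 20. With the correlations held fixed, values of 5 and 10 gave the same variance ratios.

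**One case in full.** Take baseline correlations 0.1/0.2/0.4 and visit-to-visit correlations 0.6/0.4/0.6.

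- With equal SDs the slopes are 0.1, 0.2 and 0.4, and the common slope is c = 0.261.
- Residual variance with its own slope: 400 × (1 − 0.4²) = 336.
- Excess: (0.4 − 0.261)² × 400 = 7.7.
- Ratio: 1 + 7.7/336 = 1.023.

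**Range** (power at 160 per arm; patients = 480 × excess):

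| Baseline correlation at 3 mo / 6 mo / 1-2 yr | Excess variance | Power, own slope | Power lost (points) | Patients of 480 |
|---|---|---|---|---|
| 0.3/0.3/0.3 | 0% | 84.2% | 0 | 0 |
| 0.1/0.2/0.3 | 0.8-1.0% | 84.2% | 0.3-0.4 | 4-5 |
| 0.1/0.2/0.4 | 1.6-2.5% | 87.2% | 0.6-0.9 | 8-12 |
| 0.4/0.2/0 | 4.9-6.6% | 80.4% | 2.1-2.7 | 24-32 |
| 0.5/0.3/0.1 | 5.6-8.4% | 80.9% | 2.3-3.4 | 27-40 |

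In the two fading cases, power with the common slope is about 77-79%, just below the 80.4% of the unadjusted ANOVA.

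**Simulation check.** With 160 per arm, 4000 runs per case and visit-to-visit correlations 0.6/0.4/0.6, the variance ratios were 1.00 (0.3/0.3/0.3), 1.008 (0.1/0.2/0.3), 1.048 (0.4/0.2/0) and 1.057 (0.5/0.3/0.1). The formula gives 1.000, 1.010, 1.052 and 1.060. Under the null, mean estimates from both models lay between -0.07 and 0.04 points, against a Monte Carlo standard error of 0.03 to 0.04.

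**The case against.** The best defence is that nothing here is wrong. A main-effect baseline covariate is a legitimate pre-specified choice, randomisation keeps the treatment contrast unbiased, and the unstructured covariance takes up the unexplained baseline variation, so type I error is not affected. The SAP also gives no evidence that the slopes differ. Where the baseline association is steady or strengthens over time, power with the common slope still exceeds the 80% planned: about 84% for 0.1/0.2/0.3 and 86-87% for 0.1/0.2/0.4. All of this stands, and it is why the point is minor.

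Three stronger readings are tempting, and the SAP supports none of them:

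- *The plan certainly gives up precision.* It does so only if the slopes differ, and the SAP neither shows nor excludes that.
- *The trial is underpowered.* Power falls below 80% only in the cases where a clear early association largely disappears by 1-2 years. Nothing in the SAP supports or rules out that pattern.
- *SF-36 has the same flaw.* Section 5.2.3 refers to the mixed-model approach and to imputing missing baseline scores, but writes out no model formula and no baseline SF-36 covariate. There is no stated common slope to correct.

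What the defence does not remove is the asymmetry. In large samples a visit-specific slope cannot be less efficient at 1-2 years than a shared one, and in the less favourable cases it is noticeably better.

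**Conclusion.** The point holds as a conditional matter of efficiency. As written, the primary model constrains baseline to one slope while testing at one visit. The loss ranges from nothing to about 8% of variance at 1-2 years, that is, from 0 to about 3.5 points of power, and is below one point where the baseline association is steady or strengthens only moderately over time.

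These sizes rest entirely on assumed baseline-to-follow-up and visit-to-visit correlations, complete follow-up and no centre adjustment. Missing follow-up was not modelled, although section 2.3 allows for it by enrolling 530 to obtain 480 completers. The severity is minor.

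**What to change.** In section 5.2.1.1, add a fixed baseline ATRS by visit interaction beside the visit by treatment interaction, so that each visit has its own baseline slope. Compute the estimated marginal means at a common baseline value. Make the change before outcome data are examined by treatment group, so that it cannot be taken for a data-driven revision of the primary model.

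The cost is one line of text and two degrees of freedom among about 480 completers. If the slopes turn out equal, the extra terms gain nothing.

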5.2.1.3 Assumption Checks and Alternative Analyses

Assumption checks of the fitted model will be done by visual inspection of the residuals. Marginal residuals will be plotted against the predicted marginal responses, and a check for trend will be performed. To check if the dependencies in the data has been sufficiently accounted for by the fitted

STATISTICAL ANALYSIS PLAN for the Achilles trial

model, inspection of scatter plots of conditional residuals will be done for all combinations of visits (i.e. visit 3-month vs. 6-month, 3-month vs 1-2 years and 6-month vs. 1-2 years). Normality of conditional residuals will be assessed by inspecting qq-plots for each visit.

If there are substantial deviation for normality, or there are indication of substantial residual dependence, then further random effects will be introduced in the mixed model.

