5.2.3.3 Assumption Checks

Similar as for the primary endpoint.

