5.2.3.4 Missing Data

Partially answered SF-36 questionnaires will be treated according to the SF-36v2 user's manual [13]. Note that the manual allows for a certain degree of missingness in a given questionnaire. If the manual deemed a questionnaire as not sufficiently answered, then the score value for the individual at the visit in question will be treated as a missing value, in the same manner as completely unanswered questionnaires.

Missing baseline SF-36 score data will be imputed using mean imputation (9). Missing values in follow-up SF-36 scores (at the 6-month and the 1-2 years visits) will be handled by the mixed modelling approach. However, individuals with no follow-up measurements will then be excluded from the analysis. If the proportion of patients that has no follow-up measurements is less than 5%, no action will be taken to include these in the analysis. If this proportion is larger than 5%, multiple imputation will be used to impute SF-36 scores for these individuals.

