6.3 Vital Signs

Not applicable.

7 Statistical Software

All statistical analyses will be done using R version 3.6.3 (R Core Team (2020). R: A language and environment for statistical computing. R Foundation for Statistical Computing, Vienna, Austria. URL <https://www.R-project.org/>).

8 References

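### The random intercept duplicates the unstructured correlation in the primary model, so the residual check that can alter that model is arbitrary; whether variances differ by visit is left open

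*SAP*

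**What the plan says.** SAP section 5.2.1.1 models the change in ATRS at three follow-up visits (3 months, 6 months, 1-2 years). Baseline ATRS is a covariate, not a fourth repeated measure. Two statements fix the within-patient dependence:

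- "An individual-specific random intercept term will be included in the model"
- "An unstructured correlation structure will be assumed for the repeated measurements"

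Section 5.2.1.3 then tests whether dependence has been captured: "inspection of scatter plots of conditional residuals will be done for all combinations of visits". The consequence is: "If there are substantial deviation for normality, or there are indication of substantial residual dependence, then further random effects will be introduced". No threshold is given.

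The SAP does not say whether residual variances may differ by visit. The only spread it gives is in section 2.3, "assuming a standard deviation of 20 in each treatment group". Section 7 states "All statistical analyses will be done using R version 3.6.3", with no package or function named.

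For SF-36, section 5.2.3.4 says "Missing values in follow-up SF-36 scores (at the 6-month and the 1-2 years visits) will be handled by the mixed modelling approach", and the assumption checks in section 5.2.3.3 are "Similar as for the primary endpoint". No covariance is stated for that model.

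**The concern.** An unstructured covariance for three visits already contains everything a random intercept can add. With both in the model, the data cannot say how much covariance belongs to the intercept and how much to the residuals. Conditional residuals are what remains after the predicted intercept is removed, so their pairwise correlations depend on that undetermined split. The plot meant to show whether dependence has been handled can therefore show strong dependence when the covariance is correct. The rule would then change the sole confirmatory model after the data are seen. If visit variances are free, added random effects cannot improve the fit. Under either reading they are no remedy for non-normality, the other stated trigger.

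The second issue is the variances. Read literally, an unstructured correlation can sit on a single common variance. The 1-2-year standard error would then be built partly from the spread at 3 and 6 months. If spread differs by visit, the omnibus test would miss its 5% level, in a direction the SAP's figures cannot predict.

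**Working it through.** **Inputs.** From the SAP: three visits, SD 20, 160 completers per arm, difference 7, two-sided 5%. Assumed, because the SAP gives none: visit-specific SDs, and correlations 0.6/0.4/0.6 (3-6 months, 3 months to 1-2 years, 6 months to 1-2 years). SDs are taken as residual SDs after baseline and centre adjustment.

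**Plan's own figure.** One-way ANOVA, means 0/3.5/7, SD 20: 159 per arm are needed, and power at 160 per arm is 80.4%. The planned 480 reproduces and is not affected by this point.

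**1. Parameter count.** The marginal covariance is V = τ²J + R, where τ² is the intercept variance, J the matrix of ones and R the residual covariance. Rank is that of the Jacobian of V.

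| Visits | Variances | Parameters | Rank |
|---|---|---|---|
| 3 | by visit | 1 + 3 + 3 = 7 | 6 |
| 3 | one | 1 + 1 + 3 = 5 | 4 |
| 2 (SF-36, if it mirrors the primary model) | by visit | 1 + 2 + 1 = 4 | 3 |
| 2 (same condition) | one | 1 + 1 + 1 = 3 | 2 |

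One parameter is redundant each time.

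**2. What the residual plot shows.** The conditional residuals have covariance R V⁻¹ R with R = V − τ²J, which equals V − dJ with d = 2τ² − τ⁴·(1ᵀV⁻¹1). Here 1ᵀV⁻¹1 = 1/272. For 3 months versus 1-2 years the covariance is 0.4 × 400 = 160, so the correlation is (160 − d)/(400 − d):

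| τ² | d | Correlation |
|---|---|---|
| 0 | 0 | 160/400 = 0.40 |
| 50 | 100 − 9.19 = 90.81 | 69.19/309.19 = 0.22 |
| 100 | 200 − 36.76 = 163.24 | −3.24/236.76 = −0.01 |
| 150 | 300 − 82.72 = 217.28 | −57.28/182.72 = −0.31 |

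All four rows are the same fitted model.

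The literal model was also fitted in R (nlme lme, random intercept plus corSymm; R 4.3.3, whereas the SAP names 3.6.3) to one simulated trial from six sets of starting values. With visit-specific variances, the log-likelihood (−5667.298), standard error (2.320) and omnibus chi-square (0.450) were identical from every start. The intercept variance ran from 125 to 247 and the residual correlation from −0.17 to −0.93. Across 25 simulated trials with a correct covariance, default starts gave a median of −0.73 (range −0.83 to −0.52). Normalised marginal residuals gave −0.02 to 0.03 for every visit pair.

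**3. One-variance reading, with the section 5.2.1.3 rule not acting.** The fitted common SD, s, minimises log|V| + tr(V⁻¹S), where S is the true covariance and V has one variance and free correlations. With k = s²/SD² at 1-2 years, omnibus size is P(χ² with 2 df > 5.991k) = exp(−5.991k/2), and 95% CI coverage is 2Φ(1.96√k) − 1.

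| SDs 3 m/6 m/1-2 y | s | k | Size | Coverage |
|---|---|---|---|---|
| 16/18/20 | 18.12 | 0.821 | 8.5% | 92.4% |
| 18/19/20 | 19.03 | 0.905 | 6.6% | 93.8% |
| 20/20/20 | 20.00 | 1.000 | 5.0% | 95.0% |
| 22/21/20 | 21.03 | 1.106 | 3.6% | 96.1% |
| 24/22/20 | 22.10 | 1.221 | 2.6% | 97.0% |

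Correlations of 0.4/0.3/0.5 or 0.7/0.5/0.7 move size by at most 0.2 points. Simulation with 5/7/10% missing data gave 8.1% (one variance) against 5.0% (visit-specific) at 16/18/20, and 2.9% against 4.1% at 24/22/20, with Monte Carlo SE 0.3 to 0.6 points.

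Power at 24/22/20 for means 0/3.5/7: non-centrality is 160 × (3.5² + 3.5²)/400 = 9.8. Power is 80.7% at threshold 5.991 and 72.6% at 5.991 × 1.221 = 7.32.

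**4. One-variance reading, with the rule acting.** Adding a random slope lets the variance change over visits. By the same method, size at 16/18/20 becomes 4.98% (visits coded 0/1/2) or 4.85% (coded 3/6/12 months). At 24/22/20 it becomes 4.99% or 5.0%.

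**The case against.** The strongest reply is that nothing in the primary result is shown to be wrong. The redundancy leaves the marginal covariance identified, so estimates, standard errors and tests stand. With free visit variances, even a false trigger changes no result. This is correct, and it limits the point.

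Second, the size and power figures need a reading the SAP does not state. Many statisticians use unstructured to mean the full covariance matrix, section 7 names R but no function, and a fit with corSymm and no variance function is only one transcription. The visit SDs are assumed, and with equal SDs size is exactly 5.0%. This also stands: the figures are conditional.

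Third, the two problems partly cancel. Under the one-variance reading, the section 5.2.1.3 rule could lead to a random slope, which brings size back to about 5%. This is true, but it is not a safeguard. The stated triggers are residual dependence and non-normality judged by eye, not unequal variances, and the SAP does not say which random effect would be added. It means the primary standard error under that reading would depend on a subjective look at an uninterpretable plot.

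**Conclusion.** The point holds as a specification fault that should be corrected before the analysis is run. One covariance parameter is redundant under either variance reading; this needs no assumption about the data. The pairwise check on conditional residuals is therefore arbitrary, yet it can change the only confirmatory model.

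The effect on inference is conditional. It needs the one-variance reading, spread that differs by visit, and a rule that does not act. Omnibus size then runs from 8.5% to 2.6% over the assumed SDs of 16/18/20 to 24/22/20.

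Three stronger conclusions that a reader might infer are not supported:

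- *The primary analysis is biased or invalid because of the redundancy.* It is not; the same likelihood, standard error and test result from any split.
- *The trial's type I error is inflated.* The SAP neither states equal variances nor gives visit SDs, and the error could go either way or be nil.
- *The SF-36 model has the same fault.* The SAP states no random intercept or correlation structure for it, so this holds only if it mirrors the primary model.

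**What to change.** - **Section 5.2.1.1:** delete the random-intercept sentence. Replace the correlation sentence with: *An unstructured covariance matrix with a separate variance for each visit will be assumed for the repeated measurements.* In R this is, for example, gls with corSymm plus varIdent.
- **Section 5.2.1.3:** base the dependence and normality checks on normalised marginal residuals, and delete the rule that adds random effects. The covariance is then saturated, so no dependence trigger is needed.
- **SF-36 (sections 5.2.3.1 and 5.2.3.3):** if its mixed model is meant to mirror the primary one, use the same wording for the two visits.

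The cost is SAP wording and one model line. It adds at most two variance parameters compared with the one-variance reading (one for SF-36). No data, sample size or further analysis is needed.
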